#### III. Subject Protection

#### A. IRB/ERC review

All clinical trials will be reviewed and approved by an independent IRB/ERC before being initiated at each site. Significant changes or revisions to the protocol will be approved by the IRB/ERC prior to implementation, except that changes required urgently to protect subject safety and well-being may be enacted in anticipation of IRB/ERC approval. For each site, the IRB/ERC and Merck will approve the subject informed consent form.

#### B. Safety

The guiding principle in decision-making in clinical trials is that subject welfare is of primary importance. Potential subjects will be informed of the risks and benefits of, as well as alternatives to, trial participation. At a minimum, trial designs will take into account the local standard of care. Subjects are never denied access to appropriate medical care based on participation in a Merck clinical trial.

All participation in Merck clinical trials is voluntary. Subjects are enrolled only after providing informed consent for participation. Subjects may withdraw from a Merck trial at any time, without any influence on their access to, or receipt of, medical care that may otherwise be available to them.

#### C. Confidentiality

Merck is committed to safeguarding subject confidentiality, to the greatest extent possible. Unless required by law, only the investigator, sponsor (or representative) and/or regulatory authorities will have access to confidential medical records that might identify the research subject by name.

#### D. Genomic Research

Genomic Research will only be conducted in accordance with informed consent and/or as specifically authorized by an Ethics Committee.

#### IV. Financial Considerations

#### A. Payments to Investigators

Clinical trials are time- and labor-intensive. It is Merck's policy to compensate investigators (or the sponsoring institution) in a fair manner for the work performed in support of Merck trials. Merck does not pay incentives to enroll subjects in its trials. However, when enrollment is particularly challenging, additional payments may be made to compensate for the time spent in extra recruiting efforts.

Merck does not pay for subject referrals. However, Merck may compensate referring physicians for time spent on chart review to identify potentially eligible subjects.

#### B. Clinical Research Funding

Informed consent forms will disclose that the trial is sponsored by Merck, and that the investigator or sponsoring institution is being paid or provided a grant for performing the trial. However, the local IRB/ERC may wish to alter the wording of the disclosure statement to be consistent with financial practices at that institution. As noted above, publications resulting from Merck trials will indicate Merck as a source of funding.

#### C. Funding for Travel and Other Requests

Funding of travel by investigators and support staff (e.g., to scientific meetings, investigator meetings, etc.) will be consistent with local guidelines and practices including, in the U.S., those established by the American Medical Association (AMA).

#### V. Investigator Commitment

Investigators will be expected to review Merck's Code of Conduct as an appendix to the trial protocol, and in signing the protocol, agree to support these ethical and scientific standards.

\* In this document, "Merck" refers to Merck Sharp & Dohme Corp. and Schering Corporation, each of which is a subsidiary of Merck & Co., Inc. Merck is known as MSD outside of the United States and Canada. As warranted by context, Merck also includes affiliates and subsidiaries of Merck & Co., Inc."

**Protocol/Amendment No.:** 832-01

[figure not shown]
## 12.2 List of Abbreviations

Abbreviation Details			
EZ	Ezetimibe		
Rosuvastatin	Rosuvastatin calcium		
Ros			
EZ 10 mg+Ros 2.5 mg	Co-administration of Ezetimibe 10 mg and Rosuvastatincalcium 2.5 mg		
EZ 10 mg+Ros 5 mg	Co-administration of Ezetimibe 10 mg and Rosuvastatincalcium 5 mg		
HMG-CoA	3-hydroxy-3-methylglutaryl-coenzyme A		
CHD	Coronary heart disease		
CAD	Coronary artery disease		
LDL-C	Low-density lipoprotein cholesterol		
HDL-C	High-density lipoprotein cholesterol		
JAS2012 2012 Japan Atherosclerosis Society Guidelines for Prevention of			
	Atherosclerotic Cardiovascular Diseases		

**Protocol/Amendment No.:** 832-01

## 12.3 Category Assessment for Each Patient

Subjects will be assessed using following chart based on JAS 2012.

Baseline Risk		No. of Risk Factors		
Gender	Age	
 
Hypertension
 
Smoking
 
Hypo HDL cholesterolemia (HDL-C < 40 mg/dL)
 
Family history of premature CAD in first-degree relatives (a man aged < 55 years or a woman aged < 65 years)
 
Impaired glucose tolerance
 
		
		0	Category I	
	40's	1-2	Category II	
		≥3	Category III	
Male	50's	0	Category II	
Maic		1	Category II	
		≥2	Category III	
	60's	0	Category II	
	(up to 74 years)	≥1	Category III	
	403 1 503	0-1	Category I	
Female	40's and 50's	≥ 2	Category II	
1 ciliare	60's	0-1	Category II	
	(up to 74 years)	$\geq 2$	Category III	

**Protocol/Amendment No.:** 832-01

[Instruction for this study]

· Smoking should be counted as 1 risk if patient have had  $\geq$  1 cigarette within last month.

- · Patient who is  $\geq 75$  years old should be assessed based on the criteria of 60's for each gender.
- · Male patients who are under 40's should be assessed based on the criteria of males of 40's. Female patients who are under 40's should be assessed based on the criteria of females of 40's and 50's.

[Definition of CAD by events, procedures, symptoms or imaging]

- 1. Event:
- · Myocardial infarction (MI) (e.g., subendocardial myocardial infarction, non-Q wave MI, unstable angina, acute coronary syndrome)
- 2. Procedure:
- · Percutaneous Transluminal Coronary Angioplasty (PTCA).
- · Coronary Stenting
- · Coronary Artery Bypass Graft (CABG)
- 3. Symptoms:
- · Angina (chest pain deemed to be of cardiac origin)
- 4. Imaging:
- · Angiography with evidence of CAD
- · Stress test using treadmill, echocardiography or nuclear testing consistent with CAD

Note: The above lists are not all inclusive. If your patient has a medical/physical condition and you are unsure if the condition excludes them from participation in the study, please contact the SPONSOR.

**Protocol/Amendment No.:** 832-01

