#### 4.2 Rationale

# 4.2.1 Rationale for the Trial and Selected Subject Population

Since the dosage and administration of this FDC is expected second-line therapy, FDC will be administered when patients are uncontrolled with monotherapy. Therefore, this study will be conducted to demonstrate the additional effect by comparing the efficacy between monotherapy and FDC.

The target population of this study is patients with hypercholesterolemia in whom the lipid management target value of LDL-C as per their coronary artery disease (CAD)-risk category based on JAS2012 has not been achieved, that is, patients meeting any of the following conditions, judging from the results of laboratory tests at the start of the placebo administration period and the presence/absence of CAD history.

For the hyperlipidemia patient with history of coronary artery disease (CAD), it is assumed that most of the patients are treated with lipid lowering agent based on the recommendation of JAS2012. And considering the safety of the patients, the patients who has a history of CAD or CAD-equivalent disease will be excluded from PN832 because it is considered not

MK-0653H-832-01 Final Protocol
OARDIN Confidential

**Protocol/Amendment No.:** 832-01

appropriate to stop the lipid lowering therapy for a patient with a history of CAD, and to ensure that subjects are not placed on lipid lowering therapy with lower potency than they usually receive.

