## < Visit 3: Randomization>

9. Subject meets any of the following criteria.

Category will be assessed based on Section 12.3. (JAS2012).

LDL-C value will be calculated by Friedewald method at Visit 2.

Friedewald method: LDL-C = Total cholesterol – HDL-cho – TG/5.

- (1) Subject is categorized "Category I" and has LDL-C value ≥160 mg/dL to <220 mg/dL
- (2) Subject is categorized "Category II" and has LDL-C value ≥140 mg/dL to <190 mg/dL
- (3) Subject is categorized "Category III" and has LDL-C value  $\geq$ 120 mg/dL to <160 mg/dL
- 10. Subject able to follow the instruction for drug administration and is greater than 75% compliant with study medication during the single-blind placebo run-in period.

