# Prohibited medical conditions

- 1. Subject has uncontrolled hypertension (treated or untreated) with systolic blood pressure >160 mmHg or diastolic >100 mmHg at Visit 1.
- 2. Subject has uncontrolled type 1 or type 2 diabetes mellitus (treated or untreated,  $HbA_{1C} \ge 8.0\%$  at Visit 1 or newly diagnosed within 3 months).
- 3. Subject has chronic heart failure defined by New York Heart Association (NYHA) Classes III or IV.
- 4. Subject has uncontrolled cardiac arrhythmias or recent significant abnormality in the subject's electrocardiogram as takes within 6 months prior to Visit 1 in the opinion of the investigator.
- 5. Subject has a history of coronary artery disease (CAD), CAD-equivalent disease [e.g., peripheral arterial disease, abdominal aortic aneurysm, symptomatic carotid artery disease transient ischemic attack, stroke].
- 6. Subject has familial hypercholesterolemia or has undergone LDL apheresis.

**Protocol/Amendment No.:** 832-01

7. Subject has uncontrolled endocrine or metabolic disease known to influence serum lipids or lipoproteins (i.e., secondary causes of hyperlipidemia, e.g., hyper- or hypothyroidism, Cushing's syndrome).

Note: Definitions of hyper- and hypothyroidism are as follows:

Hyperthyroidism: TSH below the central laboratory's LLN.

Hypothyroidism: TSH >20% above the central laboratory's ULN.

For subjects receiving thyroid hormone, there is no lower TSH threshold for entry (Visit 1) and the subject must be on a stable dose for ≥6 weeks before the randomization visit (Visit 3). One redraw will be allowed if the original TSH value is less than 40% above or below the reference range, but the subject must meet the criterion upon redraw.

8. Subject has estimated glomerular filtration rate (eGFR) < 30 mL/min /1.73 m^2 based on the below equation, nephrotic syndrome or other clinically significant renal disease at Visit 1.

Male eGFR  $[mL/min/1.73m^2] = 194 \times Cr[mg/dL]^{-1.094} \times age [yr]^{-0.287}$ Female eGFR[mL/min/1.73m^2]=194 x  $Cr[mg/dL]^{-1.094}$  x age [yr]  $^{-0.287}$  x 0.739

- 9. Subject has had a gastrointestinal tract bypass, or other significant intestinal melabsorption.
- 10. Subject has a history of cancer within the past 5 years from Visit 1 (except for successfully treated dermatological basal cell or squamous cell carcinoma or in situ cervical cancer).
- 11. Subject who is known HIV positive (as assessed by medical history).

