#### 5.5 Concomitant Medications/Vaccinations

Medications or vaccinations specifically prohibited in the exclusion criteria are not allowed during the ongoing trial. If there is a clinical indication for any medication or vaccination specifically prohibited during the trial, discontinuation from trial therapy or vaccination may be required. The investigator should discuss any questions regarding this with the Sponsor Clinical Director. The final decision on any supportive therapy or vaccination rests with the investigator and/or the subject's primary physician. However, the decision to continue the subject on trial therapy or vaccination schedule requires the mutual agreement of the investigator, the Sponsor and the subject.

Concurrent antihypertensive, and antihyperglycemic medications are permitted. It is preferable that doses of these medications remain stable throughout the study.

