# 6.0 TRIAL FLOW CHART

Phase	Screening (1~6 weeks)	Placebo run-in (2 weeks)	Treatment (12 weeks)		Follow up		
Week	Week -8~ -3¹	Week -2	Week 0	Week 4	Week 8	Week 12/ Discontinuati on	14 days after last dosing
Visit number	Visit 1	Visit 2	Visit 3	Visit 4	Visit 5	Visit 6	
Visit window permitted (Day) 	N/A	7~42+7	14+/-3	28+/-7	28+/-7	28+/-7	
Administrative procedure	1						
Obtain Informed Consent 	X						
Collect Medical History	X						
Review Inclusion/Exclusion criteria	X	X	X				
Review Prior/Concomitant Therapies	X	X	X	X	X	X	
Contact Patient Registration Center	X	X	X	X	X	X	
Risk assessment 	X	X	X				
Review Diet/Exercise and Instruct on JAS Guidelines	X						
Monitor Dietary/Exercise Compliance		X	X	X	X	X	
Dispense Study Drug 		X	X	X	X		
Randomized (assignment of randomization number)			X				
Monitor Medication compliance/patient diary			X	X	X	X	
Safety assessment							15
Review adverse event	X	X	X	X	X	X	X 15
Perform Physical Examination 		X				X	
Vital sign  Height/Weight 	X		X			X	
Sitting Blood Pressure/Pulse	X	X	X	X	X	X	
ECG		X					
Laboratory test 							
Lipid Panel A 	X	X	X	X	X	X	
hs CRP			X			X	
Apo protein (Apo) B			X	X	X	X	
Blood Chemistry 	X	X	X	X	X	X	
Hematology 	X					X	
TSH	X						
HbA1 C 	X					X	
Urinalysis 	X		X			X	
Pregnancy test 	X	X	X	X	X	X	

**Protocol/Amendment No.:** 832-01

1. Interval between Visit 1 and Visit 2 is determined depending on the presence of the prior treatments. Subjects washing out lipid-lowering therapy will have Visit 1 at -6 weeks from Visit 2; subjects not requiring washout will have Visit 1 at -1~-6 weeks from Visit 2 depending on the state of prior pharmacotherapy other than lipid-lowering agents in each subject.

- 2. Visit window is relative to previous Visit.
- 3. Informed consent must be obtained before any protocol-related study procedures are performed. It is allowable to obtain informed consent before Visit 1. After obtaining informed consent, subject will be given a unique screening number (refer to 7.1.1.6) and a subject identification card (refer to 7.1.1.3).
- 4. Subject's risk category assessment is determined at Visit 3 according to the Japan Atherosclerosis Society (JAS) Guideline 2012 based on the results obtained at Visit 1 and 2 (refer to Appendix 12.3).

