- 5. First dose of study drug should be taken on the day of the visit; last dose between each visit should be taken on the day before the next scheduled visit.
- 6. Auscultation and palpation and interview of condition will be conducted for physical examination.
- 7. Weight will be measured at Visit 1, 3, 6. Height will be measured only at Visit 1.
- 8. All laboratory draws for the study will be conducted after at least 10-hour fast.
- 9. Lipid panel A: LDL-C, total cholesterol (TC), HDL-C, non-HDL-C, and Triglyceride (TG)
- 10. Chemistry: Glucose, ALT, AST, ALP, uric acid, total bilirubin, BUN, CK (CPK), creatinine, Cl, potassium, sodium, γ-glutamyl transferase
- 11. Hematology: hemoglobin, platelet count, red blood cell count, white blood cell count, hematocrit
- 12. Subjects who have diagnosed with diabetes only may have their sample collected.
- 13. Urinalysis: pH, glucose (qualitative), protein (qualitative)
- 14. Urine pregnancy test (urine hCG) will be measured only in female subjects who have reproductive potential as specified in inclusion criteria #4. Urine pregnancy test (urine hCG) will be determined locally, serum β-hCG test is determined by central lab if urine pregnancy performed at the site is positive.
- 15. Post study phone call will be conducted 14 days after administration of the last dose of study drug.

Protocol/Amendment No.: 832-01

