## 12.4 Lipid Management Goals Based on Risk Assessment

Principle of the			Additional	Lipid Control (mg.	
Therapeutic Strategy	Category	Absolute Risk †	Risk ‡	LDL-C	HDL-C
Primary prevention (No history of CAD)	I	< 0.5%	No	< 160	
Drug treatment should be considered after first	t I II	< 0.5%	Yes	< 140	
improving the patient's lifestyle.		≥ 0.5%, < 2.0%	No		
	III	$\geq 0.5\%, < 2.0\%$	Yes	< 120	> 40
	111	≥ 2.0%	No/ Yes	120	≥ 40
Secondary prevention (History of CAD) Drug treatment should be considered, together with improving the patient's lifestyle.		History of CAD		< 100	

†Absolute Risk is defined as Probability of death form CAD in 10 years based on NIPPON DATA 80

Revised JAS Guidelines, 2012 version (The Japan Atherosclerosis Society)

‡ Additional Risk are defined as 1) Hypo HDL-cholesterolemia (HDL-C < 40 mg/dL), 2) Family history of premature CAD in first-degree relatives (a man aged < 55 years or a woman aged < 65 years), 3) Impaired glucose tolerance. Patient who has diabetes mellitus, chronic kidney disease (CKD), non cardio-embolic stroke or peripheral arterial disease (PAD) are definded as category III

**Protocol/Amendment No.:** 832-01

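### The chart that sets the risk category (Appendix 12.3) and the footnote to Appendix 12.4 give diabetic and CKD subjects different categories, and the category decides LDL-C eligibility

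*Combined protocol and SAP*

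**What the plan says.** Criterion 9 (Section 5.1.2) names one source for the category: "Category will be assessed based on Section 12.3. (JAS2012". Note 4 to the flow chart (Section 6.0) says that it is determined at Visit 3, "based on the results obtained at Visit 1 and 2 (refer to Appendix 12.3".

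Appendix 12.3 opens with "Subjects will be assessed using following chart based on JAS 2012". The chart crosses sex and age band with a count of five factors: hypertension, smoking, HDL-C below 40 mg/dL, a first-degree family history of early CAD, and impaired glucose tolerance. The study-specific instructions under it deal with smoking, age 75 or over and age below 40. Neither the chart nor the instructions mention diabetes or CKD.

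The footnote to Appendix 12.4 reads: "Patient who has diabetes mellitus, chronic kidney disease (CKD), non cardio-embolic stroke or peripheral arterial disease (PAD) are definded as category III". Criterion 9, note 4 and Appendix 12.3 do not refer to it.

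Diabetic subjects are expected in the trial:

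- Exclusion 2 begins "Subject has uncontrolled type 1 or type 2 diabetes mellitus", and is limited to HbA1c of 8.0% or more, or a diagnosis within the last 3 months.
- Section 5.5 states "Concurrent antihypertensive, and antihyperglycemic medications are permitted".
- Flow chart note 12, on HbA1c, reads "Subjects who have diagnosed with diabetes only may have their sample collected".
- Section 8.10 plans a diabetes subgroup.

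Exclusion 8 removes eGFR below 30, nephrotic syndrome and other renal disease of clinical significance, so a subject with eGFR of 30 or more is not excluded on that value alone. Exclusion 5 already removes stroke and peripheral arterial disease. Of the four conditions in the footnote, only diabetes and CKD therefore matter here.

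**The concern.** A subject with controlled diabetes whom the chart puts in Category I or II is in Category III by the footnote. The plan uses the category in four places:

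- the LDL-C entry window in criterion 9;
- the only stratification factor (Section 5.4);
- the risk category and time-by-risk-category terms of the cLDA model (Section 8.6.1);
- the risk-category subgroup (Section 8.10).

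The exploratory goal endpoint in Section 3.3 points to Appendix 12.4, which carries the footnote. A subject could therefore be admitted and stratified under one category and judged against the goal of another.

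The two appendices should agree. Section 4.2.1 describes the target population as patients "in whom the lipid management target value of LDL-C as per their coronary artery disease (CAD)-risk category based on JAS2012 has not been achieved", and the entry floors in criterion 9 (160, 140 and 120 mg/dL) equal the goals in Appendix 12.4 (<160, <140, <120).

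**Working it through.** No sample size, power or alpha figure in the plan depends on this point, so there is no stated figure to reproduce. The check lists the chart and compares entry windows.

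**1. Chart rows (Appendix 12.3, with its instructions for ages below 40 and 75 or over)**

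| Band | Number of factors → category | Rows | Rows in I or II |
|---|---|---|---|
| Men under 50 | 0 → I; 1–2 → II; ≥3 → III | 3 | 2 |
| Men in their 50s | 0 → II; 1 → II; ≥2 → III | 3 | 2 |
| Men 60 or over | 0 → II; ≥1 → III | 2 | 1 |
| Women under 60 | 0–1 → I; ≥2 → II | 2 | 2 |
| Women 60 or over | 0–1 → II; ≥2 → III | 2 | 1 |
| Total | | 12 | 8 |

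By single factor counts, 5 bands × 6 counts (0 to 5) = 30 cells: 3 in Category I, 11 in II and 16 in III. So 3 + 11 = 14 of 30 cells conflict with the footnote.

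**2. Diabetes counted as impaired glucose tolerance (an assumption; the plan does not say so)**

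The count is then at least 1. Nine rows remain reachable, 5 of them in I or II. By cells, 5 × 5 = 25: 1 in I, 8 in II and 16 in III, so 9 of 25 still conflict. For men aged 60 or over the conflict disappears. For women under 60 it remains at every count, because the chart has no Category III row for them.

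These counts show where the two rules disagree. They are not shares of subjects.

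**3. Entry windows (criterion 9, mg/dL): I, 160 to <220; II, 140 to <190; III, 120 to <160**

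| Chart category, against III | Eligible by chart only | Eligible under III only | Eligible under both | Range covered |
|---|---|---|---|---|
| I | 160 to <220 (60) | 120 to <160 (40) | none (0) | 60 + 40 = 100 |
| II | 160 to <190 (30) | 120 to <140 (20) | 140 to <160 (20) | 30 + 20 + 20 = 70 |

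With chart Category I, eligibility reverses over all 100 mg/dL. With chart Category II it reverses over 30 + 20 = 50 of 70. Outside the covered range both readings exclude.

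**4. Example**

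A man in his 40s has controlled diabetes, no chart factor counted and LDL-C of 170 mg/dL. By the chart he is Category I and eligible. By the footnote he is Category III and ineligible.

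**5. Goal endpoint**

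If the footnote sets the goal while the chart sets the assigned category, the thresholds differ by 160 − 120 = 40 mg/dL (I against III) or 140 − 120 = 20 mg/dL (II against III).

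**The case against.** The strongest reply is that the chart is a general rule and the footnote a specific one within the same protocol. Both appendices, criterion 9 and note 4 all cite JAS 2012, so a reader might take the footnote to override the chart. What remains would be a missing cross-reference. That may be what the sponsor intended, but no passage states it, and a site that follows criterion 9 literally is never sent to Appendix 12.4 to assign a category. Treating diabetes as impaired glucose tolerance does not settle it either: the Appendix 12.4 footnote lists impaired glucose tolerance as an additional risk and names diabetes separately, and step 2 shows that conflicts remain. The note in Appendix 12.3 about contacting the sponsor concerns whether a condition excludes a patient, not which category applies.

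Several limits do stand:

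- The category is assigned before randomization, by the same rule for all arms. Stratification and the model term work under either reading.
- The effect on the goal endpoint is conditional. Methods for exploratory objectives are left to the sSAP.
- Row and cell counts weight rare combinations equally with common ones and say nothing about frequency.
- The CKD part is weaker than the diabetes part, because the documents do not define CKD for this purpose and exclusion 8 may remove some of these patients.

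**Conclusion.** The concern holds and should be fixed. Following criterion 9 as written can admit or exclude a diabetic subject contrary to the protocol's own definition of Category III. That makes it a conflict in the text and not only missing detail. In the affected rows the choice of reading reverses eligibility over the whole of 120 to <220 mg/dL (chart Category I) or over 50 of 70 mg/dL (chart Category II).

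The conclusion rests on the chart and footnote as printed and on controlled diabetes being allowed at entry. It does not depend on how CKD is defined. The documents give no expected share of subjects with diabetes or CKD, so the number affected is unknown. Nothing here shows bias or loss of power in the primary randomized comparison. The effects shown are on who is eligible, how strata and the risk-category subgroup are labelled and, conditionally, one exploratory endpoint.

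**What to change.** Reconcile criterion 9, flow chart note 4, Appendix 12.3 and the Appendix 12.4 footnote into one category derivation. It should state how diabetes and CKD are handled and define CKD. Which rule applies is for the sponsor to decide. Cite that derivation in criterion 9, in Section 5.4 and the IVRS/IWRS specification, for the risk-category terms in Section 8.6.1, in Section 8.10, and for the goal endpoint in Section 3.3 and the sSAP.

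For subjects already randomized, keep the stratum used at randomization in the primary model. Use any reconciled category only in a supplementary or sensitivity analysis.

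The cost is a short amendment to two appendices and their cross-references, plus a check of the IVRS/IWRS and site worksheets. No added sample size is needed. No new procedure is needed for diabetes, nor for CKD if the chosen definition uses medical history and creatinine, both already collected at Visit 1. How many future subjects would change stratum or eligibility is unknown.
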